6.4 PREGNANCY

Women of child-bearing potential (WOCBP) must use an effective method of birth control during the course of the study and for 30 days following their final study visit. Allowable methods of birth control include stabilized oral contraceptive for at least three months, IUD, condom with spermicide, diaphragm with spermicide, implant, NuvaRing®, injection, transdermal patch or abstinence with a documented second acceptable method of birth control should the subject become sexually active. Females taking hormonal contraceptives must have taken the same type for at least three months (90 days) prior to entering the study and must not change type during the study. Those who have used birth control pills or hormonal contraception in the past and stopped must have discontinued usage at least three months prior to the start of the study.

A female is considered to be of childbearing potential unless she is post-menopausal (no menses for 24 consecutive months), surgically sterilized, or without a uterus and/or both ovaries.

Before enrolling any subject in this clinical trial, the Investigator must review guidelines about study participation including the topics below:

- Informed consent document
- Pregnancy prevention information
- Risks to unborn child(ren)

- Any drug interactions with hormonal contraceptives
- Contraceptives in current use
- Guidelines for the follow-up of a reported pregnancy

Prior to study enrollment, all subjects must be advised of the importance of avoiding pregnancy during participation in this clinical study and the potential risk factors for an unintentional pregnancy. The subject must sign an informed consent document stating that the above-mentioned risk factors and the consequences were discussed.

During the study, WOCBP should be instructed to contact the Investigator immediately if they suspect they might be pregnant (e.g., missed or late menstrual cycle). The Investigator must immediately notify Chiltern of any female subject who becomes pregnant any time during study participation, record the information on the Pregnancy Notification Form and email the form to Chiltern. Subjects found to be pregnant prior to Week 12 will be discontinued from the study. Chiltern will ask the site to follow-up with the subject periodically during the pregnancy for ongoing health and safety information through term, as applicable. Protocol-required procedures for the Week 12/ET evaluation must be performed for the subject.

6.5 FOLLOW-UP OF ADVERSE EVENTS

6.5.1 Follow-Up of Non-Serious Adverse Events

Non-serious AEs that are not resolved at the time of the last scheduled study visit (Week 12/ET) must be recorded in the study database as ongoing/not recovered/not resolved.

6.5.2 Follow-Up of Post Study Serious Adverse Events

Serious adverse events that are identified on the last scheduled contact (Week 12/ET) must be recorded in the study database and reported to Chiltern according to the reporting procedures outlined in Sections 6.2 and 6.3. This may include unresolved previously reported SAEs, or new SAEs. The Investigator should follow these SAEs until the events are resolved, or the subject is lost to follow-up. The Investigator should continue to report any significant follow-up information to Chiltern and the IRB up to the point the event has been resolved. Resolution means the subject has returned to the Baseline state of health, or the Investigator does not expect any further improvement or worsening of the subject's condition.

Any new SAEs reported by the subject to the Investigator that occur after the last scheduled contact and are determined by the Investigator to be reasonably associated with the application of investigational product should be reported to Chiltern and the IRB.

6.6 OVERDOSAGE

There is no specific antidote for nitric oxide. In the event of an overdose, best supportive care should be utilized. Methylene blue may be used to treat subjects exhibiting methemoglobinemia.

6.7 DISCONTINUATION OF INDIVIDUAL SUBJECTS FROM THE STUDY

Subjects who develop intolerance to the product as defined by scores of 3 (severe) on 2 or more categories of tolerability (erythema, scaling, dryness, pruritus, burning/stinging) shall be discontinued from the study.

If a subject is determined to be pregnant prior to Week 12, the subject will be discontinued from the study but followed until term.

7. STATISTICAL ANALYSIS

7.1 GENERAL CONSIDERATIONS

All statistical processing will be performed using SAS® unless otherwise stated. Statistical significance will be based on two-tailed tests of the null hypothesis resulting in p-values of ≤ 0.05 unless stated otherwise.

Continuous data will be summarized with sample size (N), mean, median, standard deviation, minimum and maximum. Categorical data will be summarized with N, frequency counts, and percentages, based on N. Data will be presented for the active treatment group and vehicle treatment group. Demographic and Baseline data will also be presented over both treatment groups.

A detailed description of the statistical methodology and data reporting for this study will be provided in the Statistical Analysis Plan (SAP). The SAP will be finalized before the database is locked and released to Novan. Any deviations from the SAP will be justified in the clinical study report.

7.2 POPULATIONS

7.2.1 Intent to Treat (ITT) Population

The intent to treat (ITT) population will include all study subjects who were randomized and dispensed study medication and grouped by the treatment to which they were assigned at randomization. All efficacy analyses will be performed on the ITT population.

7.2.2 Safety Population

The safety (SAF) population will include all randomized subjects who received at least one dose of study medication. All safety and tolerability analyses will be performed on the safety analysis population (SAF) population based on the treatments the subjects actually applied.

7.2.3 Per-Protocol Population

The per protocol (PP) population will include subjects who complete the Week 12 evaluation without noteworthy study protocol violations (i.e., any subject or investigator activity that could have possibly interfered with the therapeutic administration of the treatment or the precise

evaluation of treatment efficacy). The PP population will include subjects in the SAF population who do not meet any of the following criteria:

- Violated the inclusion/exclusion criteria;
- Have taken any interfering concomitant medications;
- Did not attend the Week 12 visit;
- Have not been compliant with the dosing regimen;
- Out of visit window at the Week 12 visit by ± 7 days.

Prior to breaking the blind, other additional criteria may be added to the list to accommodate for unforeseen events that occurred during the conduct of the trial that result in noteworthy study protocol violations. To determine dosing non-compliance criteria, the data will be reviewed in a blinded manner and a cut-point will be determined.

7.3 DEMOGRAPHIC AND BASELINE CHARACTERISTICS

Subject demographic and Baseline characteristics will be summarized by treatment group and overall for the ITT, PP and SAF populations. For continuous variables (e.g., age), mean, median, standard deviation, minimum and maximum will be presented. Categorical variables (e.g., ethnicity, race) will be summarized with frequency count and percentage by treatment group. Age will also be categorized and summarized as proportion of adults (age ≥ 18) and juvenile (age <18).

7.4 EFFICACY ANALYSIS

Efficacy of SB204 4% will be based on statistical superiority over vehicle for change from Baseline in lesion counts and improvement in IGA score at Week 12/ET.

7.4.1 Primary Efficacy Analyses

There are three co-primary efficacy outcomes:

- change in inflammatory lesions counts at Week 12/ET
- change in non-inflammatory lesions counts at Week 12/ET and
- IGA success at Week 12/ET which is defined as an IGA score of clear (0) or almost clear (1) and ≥ 2 grades less than Baseline

All three co-primary outcomes must show superiority over vehicle (p -value ≤ 0.05) in order for efficacy to be demonstrated; therefore no multiplicity adjustments will be made to the co-primary outcome analyses..

Prior to analysis of co-primary outcomes, missing post-Baseline lesion counts and IGA scores results at each visit will be imputed using a Markov chain Monte Carlo (MCMC) multiple imputation methodology. Separate multiple imputation (MI) procedures will be used for each outcome, using Statistical Analysis Software (SAS) procedure MI. Details of PROC MI and options used in the imputation procedures will be provided in a statistical analysis plan. ITT

subjects with only Baseline assessments will have the Baseline value carried forward across all visits.

The primary analyses of the co-primary efficacy endpoints will be performed in the ITT population where missing data have been imputed as described above. Additional analyses of the co-primary outcomes will be performed using the PP population. To access the sensitivity of the primary efficacy results to imputation methods, each co-primary outcome will be analyzed as described above, but with missing data imputed by last observation carried forward (LOCF) and Baseline observation carried forward (BOCF) on the ITT population.

7.4.2 Secondary Efficacy Analyses

Secondary efficacy outcomes include the percent change in inflammatory and non-inflammatory lesion counts at Week 12/ET, the median time to 35% improvement in inflammatory lesions and the time to a two or more grade improvement in the IGA.

Analysis of the secondary efficacy outcomes will be adjusted for multiplicity using a hierarchical step-down procedure. These endpoints will be tested in the specified order with the rule that once a p-value exceeds 0.05, endpoints further down in the order are not statistically significant. The order will be as follows:

- 1) Percent change in inflammatory lesions at Week 12/ET
- 2) Percent change in non-inflammatory lesions at Week 12/ET
- 3) Median time to achieve 35% reduction in inflammatory lesions
- 4) Median time to a two or more grade improvement in the IGA.

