	
statistics will be presented for the active treatment group and vehicle treatment group. Summaries over both treatment groups will be presented for demographic and Baseline characteristics.
 
Efficacy Analysis
 
Efficacy of SB204 4% will be based on statistical superiority over vehicle for change from Baseline in lesion counts and IGA score improvement at Week 12/ET.
 
Primary Efficacy Analysis
 
There are three co-primary efficacy outcomes:
 
• change in inflammatory lesions counts at Week 12/ET• change in non-inflammatory lesions counts at Week 12/ET and• IGA success at Week 12/ET which is defined as an IGA score of clear (0) or almost clear (1) and ≥ 2 grades less than Baseline. 
All three co-primary outcomes must show superiority over vehicle ($p\text{-value} \leq 0.05$) in order for efficacy to be demonstrated; therefore no adjustments for multiplicity will be made.
 
Secondary Efficacy Analyses
 
Secondary efficacy outcomes include the percent change in inflammatory and non-inflammatory lesion counts at Week 12/ET, the median time to 35% improvement in inflammatory lesions, and the median time to a two or more grade improvement in IGA.
 
Analysis of the secondary efficacy outcomes will be adjusted for multiplicity using a hierarchical step-down procedure. These endpoints will be tested in the specified order with the rule that once a p-value exceeds 0.05, endpoints further down in the order are not statistically significant.
 
Tolerability Analyses
 
Cutaneous tolerability assessments (erythema, scaling, dryness, pruritus, burning/stinging) will be summarized from Baseline to Week 12/ET. Additionally, change from Baseline in tolerability assessments will be summarized at Weeks 2, 4, 8, and 12/ET.
 
Safety Analyses
 
Adverse Events
 
All AEs that occur during the study will be recorded and classified on the basis of Medical Dictionary for Regulatory Activities (MedDRA) terminology. Treatment-emergent AEs (TEAEs) are defined as AEs with an onset on or after the date of the first study drug dose. Adverse events noted prior to the first study drug administration that worsen after Baseline will also be reported as AEs and included in the summaries.

--	---

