7.8 SAMPLE SIZE AND POWER CONSIDERATIONS

Approximately 1300 subjects will be randomized into the study in a 1:1 ratio (650 in each arm) at approximately 50 sites in North America. In the previous phase 2 study, the pooled vehicle IGA ‘success’ rate was 7.1% and the pooled SB204 IGA success rate was 13.4%. Using NQuery Advisor v7 (Statistical Solutions, Ltd) to estimate sample size and statistical power, based on a vehicle IGA success rate of 7% and a 6% difference for the SB204 arm, a sample size of 1294 was estimated to have at least 95% power for a two-sided test at the alpha=0.05 level using the continuity corrected chi-square test.

The statistical power for detecting treatment differences in inflammatory or non-inflammatory lesions exceeds 99% once at least 256 subjects are treated in each group. This is based on the following assumptions:

- For inflammatory lesions: vehicle mean change = -7.6, SB204 mean change = -14.1, and a common standard deviation = 17.1
- For non-inflammatory lesions: vehicle mean change = -5.8, SB204 mean change = -11.3, and common standard deviation = 11.8

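### The secondary step-down in Section 7.4.2 and the Synopsis is not made conditional on the three co-primaries, so error is not controlled across the two families

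*Protocol*

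**What the plan says.** Section 7.1 sets the general level: "Statistical significance will be based on two-tailed tests of the null hypothesis resulting in p-values of ≤ 0.05 unless stated otherwise".

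Section 7.4.1 gives the co-primary rule. "All three co-primary outcomes must show superiority over vehicle" at p ≤ 0.05 for efficacy to count as demonstrated, and "therefore no multiplicity adjustments will be made to the co-primary outcome analyses". That section does not say what happens to the secondary tests if a co-primary fails.

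Section 7.4.2 deals with the secondaries: "Analysis of the secondary efficacy outcomes will be adjusted for multiplicity using a hierarchical step-down procedure". It then states the rule, "These endpoints will be tested in the specified order with the rule that once a p-value exceeds 0.05", after which lower endpoints are not significant, and lists the order:

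1. percent change in inflammatory lesions
2. percent change in non-inflammatory lesions
3. time to a 35% reduction in inflammatory lesions
4. "Median time to a two or more grade improvement in the IGA"

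The Synopsis carries the same rule. Neither place mentions the co-primaries as a condition for starting.

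**The concern.** A fixed sequence protects only the tests placed in it. Here the first member is a secondary endpoint tested at the full 0.05, and the co-primary set stands outside the sequence. A failed co-primary therefore does not stop the secondary tests.

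The likely route is a trial in which the lesion counts succeed and IGA success fails. The two percent-change secondaries are close restatements of the lesion co-primaries and would probably pass, which takes testing towards the time-to-event endpoints. The last of these, time to a two-grade IGA improvement, overlaps heavily with the co-primary that has just failed. The text would allow it to be reported as a multiplicity-adjusted significant result.

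The stake is limited to secondary claims. Section 7.4.1 still requires all three co-primaries before efficacy is declared.

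**Working it through.** **The plan's own figures.** Inputs from Section 7.8: IGA success 7% v 13% ("based on a vehicle IGA success rate of 7% and a 6% difference for the SB204 arm"), 1:1 allocation, two-sided 0.05.

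Uncorrected chi-square, with mean rate 0.10:

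n per arm = [1.960 × √(2 × 0.10 × 0.90) + 1.645 × √(0.07 × 0.93 + 0.13 × 0.87)]² / 0.06² = 646.8, so 647 per arm and 1294 in total. This matches the stated total. With the continuity correction that Section 7.8 names, the same inputs give 680 per arm. That is a separate matter; it is why both versions of power appear below.

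**How each family behaves alone.** Requiring all three co-primaries at 0.05 controls the chance of wrongly declaring efficacy at 0.05. The fixed sequence controls the chance of any false secondary rejection at 0.05. Neither rule limits the chance of an error in one family or the other.

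**Error across the two families.** Scenario: both lesion effects are real and large enough that the lesion co-primaries and secondaries 1 and 2 pass; IGA success and secondary 4 are both truly null. Only errors favouring SB204 are counted, so each null test errs with probability 0.025.

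- q is the chance that secondary 3 passes, taken as independent of the IGA tests.
- ρ is the correlation between the two IGA test statistics.
- P(both) is the bivariate normal probability that both exceed 1.960.

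A false claim arises if IGA success is wrongly significant, or if it is not but secondary 3 passes and secondary 4 is wrongly significant:

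P(false claim) = 0.025 + q × (0.025 − P(both))

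| ρ | P(both) | q = 1 | q = 0.8 | q = 0.5 |
|---|---|---|---|---|
| 0.5 | 0.00462 | 0.0454 | 0.0413 | 0.0352 |
| 0.7 | 0.00827 | 0.0417 | 0.0384 | 0.0334 |
| 0.9 | 0.01482 | 0.0352 | 0.0331 | 0.0301 |

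Example: ρ = 0.5 and q = 1 gives 0.025 + (0.025 − 0.00462) = 0.0454. Simulation with 4 million draws agrees: 0.0454 and 0.0352 at q = 1, and 0.0352 and 0.0301 at q = 0.5, for ρ = 0.5 and 0.9.

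With a gate, secondary 4 can be claimed only after IGA success is itself significant in favour of SB204. Every false claim then lies inside that one event, and the probability is at most 0.025.

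Counting errors in both directions at q = 1, the ungated figures are about 0.091, 0.084 and 0.070 at ρ = 0.5, 0.7 and 0.9, against 0.05 with the gate.

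**How often the sequence would run after a failed co-primary at the planned effects.** This is not an error rate; it shows only that the situation is not remote.

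- IGA power at 650 per arm, 7% v 13%: 0.951 uncorrected, 0.941 corrected.
- Inflammatory lesions: difference 14.1 − 7.6 = 6.5, SD 17.1. 6.5 / (17.1 × √(2/650)) = 6.85, so power is above 0.9999.
- Non-inflammatory lesions: difference 11.3 − 5.8 = 5.5, SD 11.8. 5.5 / (11.8 × √(2/650)) = 8.40, so power is above 0.9999.

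The co-primary set therefore misses about 1 − 0.941 = 0.059 of the time (corrected) or 1 − 0.951 = 0.049 (uncorrected), nearly always through IGA.

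**The case against.** The strongest reply is that this belongs to the SAP. Section 7.1 says "A detailed description of the statistical methodology and data reporting for this study will be provided in the Statistical Analysis Plan", the SAP is not at hand, and a gate there would contradict nothing in Section 7.4.2. It can be added that the protocol promises adjustment only among the secondaries, which it delivers, and that a trial failing Section 7.4.1 could not sensibly make efficacy claims from secondary endpoints.

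Part of this stands. The SAP may contain the gate, and the protocol never claims control across both families. But the protocol did not leave the multiplicity rule to the SAP: it fixes the procedure, the threshold, the complete order and the stopping rule, and omits the condition for starting. Reading a gate into Section 7.4.1 is an inference, because that section ties the co-primaries only to whether efficacy is demonstrated.

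On size, the objection is fair. The inflation needs a mixed scenario; under a global null with independent tests the two-sided figure is about 0.0501. The excess in the scenario comes only from the last endpoint, after three others have passed. The more the two IGA endpoints overlap, the higher the correlation and the smaller the excess, so the 4.5% figure belongs to the low end of the assumed correlations.

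**Conclusion.** The concern holds for the protocol as written. Followed literally, Section 7.4.2 and the Synopsis let the secondary sequence run after a failed co-primary, and error across the two families is not controlled. In the scenario of real lesion effects and null IGA endpoints, the excess over 2.5% is between 0.5 and 2.0 percentage points. That range rests on an assumed correlation of 0.5 to 0.9 and an assumed 50% to 100% chance that secondary 3 passes, neither of which the protocol supplies. It is a moderate defect that should be corrected, and it does not threaten the primary conclusion.

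**What to change.** Add one sentence to Section 7.4.2 and the same sentence to the Synopsis:

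> The secondary endpoints will be tested in the order below only if all three co-primary endpoints are significant in favour of SB204 at two-sided 0.05; otherwise secondary p-values are nominal.

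If the SAP already has this gate, align the protocol with it. Make the change before unblinding, so that it cannot appear data-driven.

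Sample size, co-primary tests and secondary order stay the same, and secondary testing is unchanged whenever all three co-primaries succeed. The cost is that no formal secondary claim can be made if a co-primary fails.

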7.5 DRUG EXPOSURE AND COMPLIANCE

Drug exposure and compliance will be performed on Safety Population. The number of days that study drug was taken and study drug compliance will be summarized by treatment group.

Duration of exposure will be defined as:

(Date of Last Drug Administration – Date of First Drug Administration + 1 day) / 7 days, rounded down to an integer.

The percent compliance for SB204 will be calculated as follows and presented as follows:

% Compliance = (Number of Doses Expected – Number of Doses Missed) / (Number of Doses Expected) * 100

Where the number of doses expected is defined as the number of days from Baseline to the Week 12/ET visit. Subject's diaries will be reviewed at each visit to report the number of doses that were missed.

Percent compliance will be summarized by frequency count and percentage of subjects with compliance as defined in the SAP. Percent compliance will also be summarized as a continuous variable using descriptive statistics.

7.6 TOLERABILITY

Cutaneous tolerability assessments (erythema, scaling, dryness, pruritus, burning/stinging) will be summarized by visit from Baseline to Week 12/ET by treatment group. The proportion of subjects in each treatment group who shift scores from Baseline at each visit will also be summarized.

7.7 SAFETY

7.7.1 Adverse Events

All AEs that occur during the study will be recorded and classified on the basis of Medical Dictionary for Regulatory Activities (MedDRA) terminology. Treatment-emergent AEs (TEAEs) are defined as AEs with an onset on or after the date of the first study drug dose. Adverse events noted prior to the first study drug administration that worsen after Baseline will also be reported as TEAEs and included in the summaries.

All information pertaining to an AE noted during the study will be listed by subject, detailing verbatim term given by the Investigator or designee, preferred term, SOC, onset date, resolution date, severity, seriousness, action taken, outcome, and drug relatedness. The event onset will also be shown relative (in number of days) to date of first dose.

Treatment-emergent AEs will be summarized by treatment group, the number of subjects reporting a TEAE, SOC, preferred term, severity, relationship to study drug (causality), and seriousness. When summarizing AEs by severity and relationship, each subject will be counted only once, within a system organ class or a preferred term, by using the event with the highest severity and greatest relationship within each classification.

Serious AEs will be summarized by treatment group, severity, and relationship to study drug, and individual SAEs will be listed by subject. In addition, a list of subjects who prematurely discontinue from the study due to an AE will be provided.

